**Hypotheses:**

- 1a. Participants with LLA will exhibit significantly increased endurance (as evidenced by an ability to walk significantly further in a timed walking test) wearing the mRSF compared to the ESF.
- 1b. Participants will report significantly reduced levels of exertion after performing a timed walking test in the mRSF, compared to the ESF.
- 2a. Participants will report significantly increased mobility, balance confidence, and health and significantly decreased fatigue when using the mRSF, compared to the ESF.
- 3a. Use of the mRSF will significantly reduce participants' net energy cost of walking (ECW) at slow, comfortable, and fast walking speeds, compared to the ESF.

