**B. RESEARCH PROCEDURES INVOLVED.**

1. Provide a complete description of: a. the study design, and b. sequence and timing of all study procedures that will be performed, e.g., volume of blood, size of biopsy, drug administration, questionnaire, name of psychological test. Provide this information for each phase of the study (pilot, screening, intervention and follow-up). **Use lay language.** Attach study flow sheet, if available.

We will conduct a study to compare endurance, walking performance, mobility, and perceived exertion of participants with transtibial amputation wearing two different prostheses: (1) a prosthesis with a modified Running Specific Foot (mRSF), and (2) a prosthesis with a Energy Storing Foot (ESF). To maximize study resources, we will recruit participants who will be receiving from their prosthetist the mRSF prosthesis as part of their normal clinical care. We will fabricate a duplicate prosthesis with the ESF as part of this study to be used as a comparison.

*Note: Both the mRSF and ESF included in this study are devices that people with LLA use daily in their normal lives outside of this study. These feet (and other components included in the prostheses created for this study) are class I devices and exempt from U.S. Food and Drug Administration premarket notification procedures.*

We will conduct a randomized crossover study to compare endurance, energy expenditure, and reported health of participants with transtibial amputation wearing prostheses with the mRSF and ESF described above. Study participants will be randomly assigned to the first foot condition (i.e. ESF or mRSF). To standardize test conditions, the participant's prosthetist ([name]) will fabricate two comparable prostheses with identical (i.e. duplicated) prosthetic sockets, interfaces, and suspension mechanisms. The same socket cannot be used for both prostheses because of the unique, direct-lamination attachment of the mRSF to the socket. The duplicate socket will be fitted with common ESF, the Ossur Vari-flex foot. We have obtained written commitments from Ossur to donate prosthetic components and from Davidson Prosthetics to donate time and materials needed to fabricate the duplicate sockets and test prostheses. Participants will be asked to wear the same athletic shoes for all sessions in order to standardized footwear between tests.

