Participants will be recruited from their local prosthetist's office (Davidson Prosthetics, Federal Way, WA). Davidson Prosthetics is the sole location for recruitment as this is the only provider of the mRSF in the Northwestern United States.

Participants will be asked to come to the University of Washington Assessment and Training Laboratory (ATL) for three test sessions. Participation in the study will require participants attend three visits over the course of about three months, totaling approximately 7.5 hours.

Session 1: At the first session, we will screen participants, explain the study to them, and obtain informed consent (**Appendix 1**). Participants who agree will then be administered a baseline survey and perform initial speed testing. The baseline survey will include non-identifiable, medical, and demographic questions we will use to characterize the study sample (**Appendix 2**). Participants will then be asked to walk on a treadmill for 6 minutes to determine their comfortable walking speed. The treadmill is equipped with full-length handrails that allow the participant to steady him/herself as needed. A researcher will be next to the subject at all times to assist the subject if he or she were to become distressed.

Participants will be given blinded control of the treadmill speed for the first 30 seconds of testing in order to select their preferred speed. Each participant's comfortable speed will be noted and used as a reference for the metabolic testing (see Session 2 and 3, described below). Slow and fast speeds will be self-selected using an identical method (blinded control of the treadmill adjustment). Participants will be asked to perform a 6 minute practice trial at their self-selected fast speed to ensure the participant is capable of sustaining the speed without undo stress. If a participant is unable to sustain the set speed for the entire 6 minutes, he/she may reduce speed as desired, and a weighted average of the start and end fast speeds will be used for treadmill testing in Sessions 2 and 3. We will also give participants a step activity monitor to wear on their prosthesis. The activity monitor is a small, unobtrusive sensor about the size of a pager that is worn on the prosthesis and measures steps taken by the participant while they are away from the lab. Participants will be shown how to attach the activity monitor to their prosthesis by study investigators. Session 1 is expected to take about 1.5 hours.

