Session 2: The second session will be performed after participants use the randomly-assigned ESF or mRSF prosthesis for a period of 1 month. Upon arrival at the lab, study

staff will remove the activity monitor and ask the participant to complete a self-report survey (**Appendix 2**) to evaluate their perceived performance, health, and satisfaction with their prosthesis. The survey will be administered on a tablet computer (iPad) and includes the following standardized instruments selected to measure participants' mobility, fatigue, balance confidence, activity restrictions, and satisfaction:

- Prosthetic Limb Users Survey of Mobility - PLUS-M measures respondents' self-reported mobility with a prosthesis. The PLUS-M was developed by the investigators in a prior study to address methodological limitations present in existing mobility measures. We will administer the PLUS-M computer adaptive test (CAT) to achieve the greatest precision of measurement and ease respondents' burden (i.e., CAT requires participants answer fewer questions than would taking the entire survey).
- PROMIS - Fatigue - PROMIS-F measures symptoms and effects of fatigue on respondents' ability to execute daily activities over a 1-week recall period. We will also administer PROMIS-F by CAT.
- Activities Specific Balance Confidence Scale - ABC measures respondents' confidence in performing basic ambulatory activities. We will administer a version of the ABC recommended to ease administration and improve scoring. All 16 questions of the ABC will be administered (CAT not available).
- Trinity Amputation and Prosthesis Experience Scales - Revised - TAPES-R is a multidimensional health instrument that measures activity restrictions and satisfaction with a prosthesis. We will administer 19 TAPES-R questions (CAT not available).

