Participants will remove the K4b2 monitor and conduct the 6MWT according to the protocol described above. After completing the Borg RPE, the participant will re-don the K4b2 monitor and sit quietly in order to return to their resting VO2 rate.

Participants will begin the treadmill testing once they have returned to their resting VO2 rate.

Participants will walk for 6 minutes on the treadmill at comfortable, slow, and fast walking speeds (as determined in Session 1). The order of the speeds will be randomized within-subjects to control for fatigue. This randomized order will be carried over into the third session so that participants are tested in the same order both times. Walking VO2 consumption rate (ml/min) will be averaged over the final 1 minute period of each activity. Participants will rest at least 5 minutes between each walking trial in order to return to their resting VO2 rate.

Session 2 will require about 3.0 hours to complete. Upon conclusion of Session 2, participants will transition to the second prosthesis (ESF or mRSF, depending upon randomization) and will be asked to use it exclusively for 1 month before returning for Session 3.

Session 3: The third session will be identical to the Session 2, but will be conducted with participants using the alternate prosthesis (e.g., ESF if they were previously tested in the mRSF).

2. Would subjects undergo these or similar procedures (medical, psychological, educational, etc.) if they were not taking part in this research?  No  Yes If "Yes," describe how the study procedures differ from what subjects would otherwise undergo.

The study procedures include outcome measures (survey measures, 6MWT, or Borg RPE) that a prosthetist might perform in a clinic to evaluate a patient's performance with a new prosthesis. However, the Cosmed K4b2 portable metabolic analysis system and treadmill walking are unlikely to occur in normal prosthetic clinical practice. These procedures are more likely to be conducted as part of a physical therapy treatment plan and would not be considered unusual procedures at a physical therapy clinical visit.

3. Check all of the boxes below that apply to your research:

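### Does stating exclusive wear only for the second crossover month undermine the self-report comparison of the two feet?

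*Protocol*

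**What the plan says.** The design in protocol section VIII.B.1 is a randomized two-period crossover of the energy storing foot (ESF) and the modified running foot (mRSF), with one month on each before testing. Two sentences describe the months of wear.

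- Before Session 2: "The second session will be performed after participants use the randomly-assigned ESF or mRSF prosthesis for a period of 1 month".
- Before Session 3: participants move to the second leg and "will be asked to use it exclusively for 1 month before returning for Session 3".

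The Session 1 text gives no wear instruction for the first month. It does introduce the step monitor: "We will also give participants a step activity monitor to wear on their prosthesis". On arrival at Session 2, "staff will remove the activity monitor", and the next visit is covered by "The third session will be identical to the Session 2".

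The outcomes most exposed to daily wear are the self-reports. Hypothesis 2a reads: "Participants will report significantly increased mobility, balance confidence, and health and significantly decreased fatigue when using the mRSF, compared to the ESF". One of its instruments, PROMIS-Fatigue, asks about fatigue and the ability to "execute daily activities over a 1-week recall period". The mRSF leg reaches participants through routine care, since the plan is to "recruit participants who will be receiving from their prosthetist the mRSF prosthesis as part of their normal clinical care". The ESF leg is a duplicate made for the study.

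**The concern.** A crossover compares two treatments within a person under like exposure. Here the word *exclusively* is attached to the second month only. Participants have used a prosthesis for more than a year (section VIII.D, inclusion criteria), so an older leg may be at hand. The protocol does not say that it is set aside, or that the other study leg is held back during the first month.

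If some first-month wear were on another leg, answers about daily mobility, balance confidence and fatigue would partly describe that leg, and the hypothesis 2a contrast would no longer be a clean comparison of the two feet. With at most 24 completers, avoidable dilution would be unwelcome, and no analysis can restore exposure afterwards. A lesser point is that no step is written for re-attaching the step monitor for the second month.

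**Working it through.** **What the two sentences do.** The Session 2 sentence answers the question of when the session is held: after a month on the assigned leg. It tells participants nothing. The sentence at the end of Session 2 is the only wear instruction in the text, and it comes at the switch of legs, where a reminder to use only the new one is natural. The text therefore contains one instruction and one silence, not two conflicting rules. The Session 2 sentence is fully compatible with wearing the assigned leg alone.

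**What could follow if another leg were worn in the first month.** The documents give no figure to reproduce, so this is algebra on assumed quantities.

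- A and B are the mean self-report scores on mRSF and ESF, and δ = A − B.
- uA and uB are the shares of first-month experience spent on another leg by those starting on mRSF and on ESF.
- XA and XB are the scores on that other leg for the same two groups.
- Scores mix in proportion to wear, and the second month is exclusive.

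The within-person differences, mRSF minus ESF, are then:

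- mRSF first: (1 − uA)A + uA·XA − B = δ − uA(A − XA)
- ESF first: A − (1 − uB)B − uB·XB = δ + uB(B − XB)
- Crossover estimate (mean of the two): δ − [uA(A − XA) − uB(B − XB)]/2

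**Special cases.**

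1. No other leg (uA = uB = 0): the estimate is δ, and nothing is lost.
2. A third leg O in both groups with equal share u: δ − u(A − B)/2 = δ(1 − u/2). The level of O cancels, because it enters both first-month means alike and is removed as a period effect. For u = 0.1, 0.3 and 0.5 the factor is 0.95, 0.85 and 0.75.
3. The other study foot in both groups (XA = B, XB = A) with equal share u: δ(1 − u), giving 0.90, 0.70 and 0.50 for the same u. If this happens in one group only, the factor is 1 − u/2.
4. A third leg worn only by those starting on ESF (uA = 0): δ + uB(B − O)/2. With A = 1, B = 0, O = −1 and uB = 0.3 this is 1 + 0.3 × 1/2 = 1.15, larger than the true contrast of 1.

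The loss thus runs from nothing to half over an assumed range of u, and case 4 reverses the direction. Movement toward zero is assured for a third leg only if the shares are equal, and nothing in the documents fixes u, its equality between sequences, or which other leg would be worn.

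**Which outcomes are reached.** The 6-minute walk, the Borg rating after it and the oxygen measurements are made in the laboratory on the study leg, so hypotheses 1a, 1b and 3a could be touched only through acclimation. For PROMIS-Fatigue, only wear in the last week before the session counts. Satisfaction, which TAPES-R also measures, is not named in hypothesis 2a.

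**The monitor.** If Session 3 repeats Session 2, it includes taking the monitor off on arrival, so wear during the second month is implied. No stated hypothesis uses step counts.

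**The case for a change.** The best argument for a change is that wear is trial conduct and not something to leave to an analysis plan. The protocol already states the condition for one month, the Session 1 text is where the matching statement would sit, and it is absent. Calling Session 3 identical to Session 2 describes the test visit, not the month before it. Experienced users plausibly own another leg, the sample is small, and the remedy would be about one sentence. Possible imbalance between the sequences could also be used as an argument for aligning the periods.

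Much of this stands as description. Exclusivity is indeed written for one month only, and the effect on self-reports is possible in principle. What does not stand is the step from silence to a different exposure. Nothing in the text says that participants hold both study legs in the first month. The larger losses in case 3 need participants who start on mRSF to wear the duplicate ESF leg a month early, which nothing suggests. Section VIII.H.3 has the team collect delivery schedules and problems with fit and function from the prosthetist, so part of what happens with the legs will be known. What participants are told may also be in the consent form (Appendix 1), which is not in the text at hand.

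**Conclusion.** No change to the plan is needed. This is a missing detail that investigators fill sensibly: a month of using the randomly assigned leg is ordinarily understood as wearing that leg, and the same condition would be applied in both months of a crossover. No rule in the protocol produces a wrong result, and the only possible amendment would write down an instruction whose content is for the sponsor to decide. If the protocol is reopened for another reason, bringing the two sentences into line is a harmless tidying of wording.

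The size of any effect cannot be stated from the documents. It is zero if the assigned leg is worn in both months. Otherwise it depends on an assumed share of wear on another leg and on whether that share is equal in the two sequences. It concerns mainly the hypothesis 2a self-reports. The monitor point needs nothing further. This conclusion assumes that the participant materials not shown do not permit wear of another leg in the first month.

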**Drug administration**

- Administration of a drug (either FDA-approved or investigational) for research purposes to a subject-patient during general or regional anesthesia.
- Administration of a drug (either FDA-approved or investigational) for research purposes to a subject-patient during the 1.5 hours preceding general or regional anesthesia.

**Blood lines**

- Inserting an intravenous (central or peripheral) or intra-arterial line for research purposes in a subject-patient during general or regional anesthesia.

**Sample collection**

- Obtaining samples of blood, urine, or cerebrospinal fluid for research purposes while a subject-patient is under general or regional anesthesia.
- Obtaining a research sample from tissue or organs that would not otherwise be removed during surgery, while the subject-patient is under general or regional anesthesia.

**Radio-isotopes**

- Administration of a radio-isotope for research purposes during the 3 hours prior to anesthesia or while a subject-patient is under general or regional anesthesia.

If you checked this box, you are responsible for informing in advance all appropriate clinical personnel (e.g., nurses, technicians, anesthesiologists, surgeons) about the administration and use of the radio-isotope, to ensure that any personal safety issues (e.g., pregnancy) can be appropriately addressed. This is a condition of IRB approval.

**Experimental devices**

- Implantation of an experimental device while a subject-patient is under general or regional anesthesia.

**Other experimental manipulations or procedures**

- Other manipulations or procedures performed solely for research purposes while a subject-patient is under general or regional anesthesia (e.g., experimental liver dialysis, experimental brain stimulation)

**None of the above**

None of the above apply to my research

## 4. If you checked any box in question #3 except "none of the above", answer the following questions:

a. Provide the name and institutional affiliation of the physician anesthesiologist who is a member of your research team or who will serve as a safety consultant about the interactions between your research procedures and the general or regional anesthesia of the subject-patients. If your procedures will be performed at a UW Medicine facility or affiliate, the anesthesiologist must be a UW faculty member.

N/A

b. If you have not yet consulted with an appropriately qualified person about this issue, describe in detail your plans to do so. The IRB will not approve your application without this consultation. If UW Department of Anesthesiology approval has been obtained, please provide the Department's letter of support.

N/A

## 5. Required application supplements. Complete and attach the indicated SUPPLEMENT, as appropriate

a. **SUPPLEMENT: Drugs, Biologics, Botanicals** – for research involving the use of any of the following:

- Drugs regulated by the FDA (prescription, over-the-counter, approved, or investigational)
- Biologics regulated by the FDA (prescription, over-the-counter, approved, or investigational)
- Botanicals
- Dietary Supplements

b. **SUPPLEMENT: Devices** – for research involving the use of any medical device (approved or investigational; including software used with a medical device, and including mobile medical applications).

See attached (**Appendix 3**) .

c. **SUPPLEMENT: Genetic Research** – submit this supplement when your research involves genetics. **Genetic research** is defined as research involving the analysis of any of the following: DNA; RNA; chromosomes; mitochondria; any or all parts of the human genome; or biomarkers such as proteins or metabolites which may be implicated in, associated with, or cosegregated with a disorder, syndrome, condition, or predisposition to disease or behavior. Usually genetic research involves the collection and/or use of human biological specimens such as blood, skin, or other tissues, nail clippings, or hair. Genetic research may also include the construction of pedigrees ("maps" of the distribution of a particular trait or condition among related individuals) or family medical histories.

d. **SUPPLEMENT: Department of Defense** – for research involving any component of the federal Department of Defense (DOD). "Involvement" means funding; collaboration or cooperative arrangements; use of facilities, resources, or personnel; use of military or civilian members of the DOD (or their records/specimens) as subjects.

e. **SUPPLEMENT: Department of Justice** – for research involving the federal Department of Justice (DOJ) or any of its components (such as the National Institute of Justice, or any facilities/personnel of the Bureau of Prisons). "Involvement" means funding; collaboration or cooperative arrangements; use of facilities, resources, or personnel; use of records or specimens from DOJ employees or from prisoners in any Bureau of Prisons facility.

f. **SUPPLEMENT: GWAS dbGaP** – for research that will involve submitting data to the federal Database of Genotyped and Phenotyped (dbGaP) information.

g. For research involving the **Department of Energy (DOE)**, researchers should consult the **CHECKLIST Department of Energy** to ensure that they have addressed all DOE requirements. However, the Checklist does not need to be completed and submitted unless the researcher believes it would be a useful attachment.

**C. DECEPTION:** If any deception or withholding of complete information is required for this activity, explain why this is necessary and attach a protocol explaining if, how, when, and by whom subjects will be debriefed.

No deception is required for this study.

**D. SUBJECTS**

The IRB reviews the number of subjects you plan to study in the context of risks and benefits. If your research is approved for a specific number of subjects, the data from any "extra" subjects cannot be described as having been obtained with IRB approval.

See the HSD website for the definition of "human subject" <http://www.washington.edu/research/hsd/docs/1253>. Before answering the questions below, be sure that you are familiar with the definition.

1. **Subject groups/categories and numbers.** Complete this table by listing:

- Your groups or categories of subjects. "Group" should be defined as appropriate for your research.
  - **"Units" within a group.** For most research, a group will consist of individuals, such as children aged 8-12, or individuals with high blood pressure. However, this will not be true for all research. Examples of groups with "units" that are not individuals:
    - Dyads such as Alzheimer's-patient-and-caregiver, with one group of the dyads assigned to one intervention (e.g., behavioral modification) and another group of the dyads assigned to a comparison intervention(e.g., drug treatment).
    - Families. For example, a study of mental health interventions for homeless families might have one group of 30 families assigned to one intervention and another group of 30 families assigned to a different intervention.
    - Other. For example, the "units" in autism research might be an autistic individual and all his/her living blood relatives. The units in an academic excellence study might be a student-parents-teacher unit.
  - **Types of groups.** There are many ways in which subjects might be grouped. Examples:
    - By intervention. Example: research comparing two different drugs for high blood pressure.
    - By subject population. Example: research comparing the incidence of domestic violence in families living in urban settings versus families living in rural settings.
    - If you have only one group, fill in only one line in the table. Add more lines if needed.
- The age range of each group.
- The upper limit/number of **completed** subjects you need for each group. *Completed means that all research procedures involving the subjects or the obtaining of specimens/records/data have been completed as far as is possible for each subject, including any follow-up (such as follow-up access to medical records.) In some cases, such as an online survey, it is not possible to predict the number of subjects who will complete the research. If you cannot predict or describe the maximum number of subjects you need in each group, check the appropriate box and provide your rationale in the space provided below the table.*

Group name/description	Age range of subjects	Maximum desired number of individuals (or other group unit, such as families) who will complete the research.*	Cannot provide a number.**
People with lower limb loss	>18	24	 **
			 **
			 **
			 **

\*This is the number of subjects (individuals, dyads, families, etc., as appropriate) in each group that will be considered for approval by the IRB.

\*\*If you cannot predict or describe the maximum number of subjects you need in each group:

Provide your rationale and description of research scope here. *Include any information or estimates you might have about the number of subjects, so that the IRB has a sense of the scope of your research. For example, your research might be a small pilot study of all patients presenting with a rare disease at UW Medicine in the next year. Or, it might involve a survey posted on Craig's List for two weeks that could result in thousands of responses.*

N/A

**NOTE: In your periodic Status Report, you will be asked to complete the table below with your subject numbers. While developing your research protocol, please plan ahead so that you will have an accurate record of the subject numbers above. This is for illustration only. Do not complete this table.**

Group Name / Description	# Completions			# Ongoing (subjects still involved)	# Withdrawals, drops, lost		
	Total approved by IRB	A At time of last Status Report	B Since last Status Report		C At time of last Status Report	D Since last Status Report	C + D Total to date

**2. Explain how you will achieve equitable subject representation in the following categories. If not applicable, justify exclusions.**

